### 7.3.3 Height and Weight

Height in centimeters (cm) and body weight (to the nearest 0.1 kilogram [kg] in indoor clothing, but without shoes) will be measured as indicated in [Table 7-1](#).

### 7.3.4 Laboratory Evaluations

All laboratory parameters assessed for safety purposes will be evaluated locally. Refer to [Table 7-3](#) for a summary of the parameters to be evaluated according to [Table 7-1](#). On dosing days of IMCgp100, samples for these parameters will be collected prior to the infusion of IMCgp100.

More frequent evaluations may be performed at the investigator's discretion if medically indicated; results should be recorded as unscheduled laboratory assessments.

The Sponsor or the designated contract research organization (CRO) will be provided with a copy of the laboratory certification and tabulation of the normal ranges for each parameter required. In addition, if at any time a patient has laboratory parameters obtained from a different outside laboratory, the Sponsor or the CRO must be provided with a copy of the certification and a tabulation of the normal ranges for that laboratory.

**Table 7-3 Local Clinical Laboratory Parameters Collection Plan**

Test Category	Test Name
Hematology	Hematocrit, hemoglobin, platelets, white blood cells with differential (basophils, eosinophils, lymphocytes, monocytes, neutrophils)
Chemistry	Albumin, alkaline phosphatase, alanine transaminase, aspartate transaminase, bicarbonate, calcium, chloride, creatinine, glucose magnesium, inorganic phosphate, potassium, sodium, total bilirubin (also measure direct and indirect bilirubin if total bilirubin is > grade 1), blood urea nitrogen or urea, amylase, and lipase
Cytokines	

**Hematology:** The panels outlined in [Table 7-3](#) will be performed as per the assessment schedule in [Table 7-1](#).

**Clinical chemistry:** The panels outlined in [Table 7-3](#) will be performed as per the assessment schedule in [Table 7-1](#).

**Cytokine analysis panel:** The cytokine panel outlined in [Table 7-3](#) will be performed on an as needed basis in case a patient has an AE suspected to include cytokine release syndrome. This assessment should be performed at the following time points:

- [REDACTED]
- [REDACTED]

**Pregnancy and assessment of fertility:** Pregnancy tests will be performed for women of child bearing potential. At Screening, a serum pregnancy test must be performed within 72 hours before the first dose of IMCgp100. During the study (Day 1 of each cycle starting with Cycle 2), a serum or urine pregnancy test must be performed. At EOT, a serum or urine pregnancy test must also be performed. Pregnancy will be reported through the Pregnancy Reporting Form (paper) as well as in the eCRF as an AE.

**Cardiac assessments:** A standard 12-lead ECG will be performed as per the assessment schedule in [Table 7-1](#). ECG assessment is performed at Screening prior to the first dose and at EOT assessment. Clinically significant abnormalities present at Screening should be reported on the Medical History eCRF page. New or worsened clinically significant findings occurring after informed consent must be recorded on the AE eCRF page.

### 7.3.5 Immunogenicity Assessments

The immunogenicity blood samples should be taken according to [Table 7-1](#). Details are also described in the laboratory manual for the handling, labelling, and shipment of immunogenicity blood samples. The blood samples should be collected immediately before IMCgp100 infusion, and it is essential that the actual time and date of collection be recorded on the patient's eCRF.

## 8 ADVERSE EVENTS AND SAFETY REPORTING

### 8.1 Assessment of Safety

All patients who receive any treatment with IMCgp100 will be considered evaluable for safety. All AEs, regardless of study drug relationship, will be collected through the 90-day Safety Follow-up Period. At the time of consent, if any patient has any ongoing AE(s) from the parent IMCgp100 study, the AE(s) will be captured on the eCRF page and the "Ongoing at Start of Study" must be answered "Yes". The start date recorded in the eCRF for the rollover study should be equal to the start date of the event as recorded in the parent study. Timely, accurate, and complete reporting and analysis of safety information from clinical studies are crucial for the protection of patients and is mandated by regulatory agencies worldwide. The Sponsor and CRO have established standard operating procedures in conformity with regulatory requirements worldwide to ensure appropriate reporting of all safety information. All clinical studies conducted by the Sponsor or its affiliates will be conducted in accordance with those procedures.

Individual AEs should be evaluated by the investigator and should be reported to the CRO/Sponsor for evaluation. This includes the evaluation of the event's seriousness and the causality between the investigational medicinal product(s) and/or concomitant therapy and the AE. The CRO/Sponsor is required to maintain detailed records of all AEs reported by the investigator(s) and to perform an evaluation with respect to seriousness, causality, and expectedness. On request of a competent authority in whose territory the clinical trial is being conducted, the Sponsor should submit detailed records of all AEs which are reported by the relevant investigators. Case report processing concerns evaluation of data in individual cases, identification of individual cases requiring specific handling, recognition and processing of alerts, and any other data processing of aggregated cases.

#### 8.1.1 Definitions

Definitions of AEs, adverse drug reactions, SAEs, unexpected adverse drug reactions, and AEs of special interest (AESI) are presented below.

**AE:** An AE is defined as the appearance of (or worsening of pre-existing) an undesirable sign, symptom, or medical condition that occurs after patient's signed informed consent has been obtained. Abnormal laboratory values or test results occurring after informed consent constitute AEs only if they induce clinical signs or symptoms, are considered clinically significant, require therapy (eg, hematologic abnormality that requires transfusion or hematological stem cell support), or require changes in study medication.

**Adverse drug reaction:** An adverse drug reaction is an unwanted or harmful reaction which occurs after administration of a drug or drugs and is suspected or known to be due to the drug. Adverse drug reactions have traditionally been categorized as pharmacologic (predicted based on the pharmacology of the drug) or idiosyncratic (not predicted based on pharmacology).

**SAE:** A SAE is any AE that is defined as 1 of the following:

- Is fatal or life-threatening
- Results in persistent or significant disability or incapacity
- Constitutes a congenital anomaly/birth defect
- Is medically significant, ie, defined as an event that jeopardizes the patient or may require medical or surgical intervention to prevent 1 of the outcomes listed above
- Requires inpatient hospitalization or prolongation of existing hospitalization, unless hospitalization is for:
  - Routine treatment or monitoring of the studied indication, not associated with any deterioration in condition
  - Elective or pre-planned treatment for a pre-existing condition that is unrelated to the indication under study and has not worsened since signing the informed consent
  - Treatment on an emergency outpatient basis for an event not fulfilling any of the definitions of a SAE given above and not resulting in hospital admission
  - Social reasons and respite care in the absence of any deterioration in the patient's general condition
- Death due to the progression of malignancy should not be reported as a SAE, if documented by use of appropriate method (eg, as per Response Evaluation Criteria in Solid Tumors v.1.1.1). Any AE that occurred as a result of the PD should be reported in the appropriate manner

**Unexpected adverse drug reaction:** An adverse drug reaction that is not consistent with applicable product information or characteristics of the study drug.

**Suspected, unexpected, serious adverse reaction (SUSAR):** A SUSAR is an adverse reaction meeting serious criteria (above), the nature or severity of which is not consistent with the reference safety information for the investigational drug(s).

**AESI:** An AESI (serious or non-serious) is an AE with scientific and/or medical concern specific to the Sponsor's program, for which ongoing monitoring and rapid communication by the investigator to the Sponsor can be appropriate. Refer to the IMCgp100 Investigator's Brochures for details of the AESI.

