## **AMENDMENT 2**

### **Amendment Rationale**

The pattern of clinical response to immunotherapeutic agents differs from that observed with cytotoxic therapies. There is accumulating evidence that a proportion of patients with advanced melanoma treated with immunotherapy agents, including IMCgp100, may develop initial radiographic progression of the tumor before demonstrating meaningful clinical benefit. This delayed response to therapy or immune-mediated tumor flare have been coined as “pseudo-progression” that can then be followed by prolonged periods of disease stabilization or objective tumor responses. To allow for patients to continue therapy beyond an initial assessment of progressive disease according to RECIST v1.1, this amendment provides additional detail delineating criteria for treatment beyond progression. Patients must meet specific clinical criteria and provide additional informed consent to continue therapy beyond an initial assessment of disease progression.

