### 6.6.1 Criteria for Treatment Beyond Initial RECIST v.1.1 Disease Progression

Imaging studies will be performed on all patients to monitor for disease progression using RECIST v1.1 criteria. Upon disease progression by standard RECIST v.1.1 criteria, treatment beyond progression is an option.

Clinical evidence suggests that a minority of patients treated with immunotherapies, including IMCgp100, will derive clinical benefit after an initial assessment of PD. For patients in the IMCgp100 arm, if PD based on RECIST v.1.1 occurs, treatment may continue according to the protocol-specified regimen until 1 of the following criteria is met:

1. Unequivocal, confirmed PD based on immune-related Response Evaluation Criteria in Solid Tumors (irRECIST) (guidelines based on Wolchok, 2009; Nishino, 2013; and Bohnsack, 2014): An initial assessment of PD by RECIST v.1.1 (initial PD assessment) will be confirmed with a repeat radiologic evaluation will be performed at least 4 but no more than 12 weeks later as scheduled per protocol. For patients who continue IMCgp100 therapy beyond initial PD, unequivocal, confirmed PD is defined as an additional 20% increase in tumor burden (sum of diameters of both target and new lesions) from the initial PD assessment
2. Meets any of the investigational product discontinuation criteria ([Section 6.6](#) above)
3. Clinical symptoms or signs indicating clinically significant PD (not meeting radiologic PD) such as decline in ECOG performance status or the benefit-risk ratio of continuing therapy is no longer justified
4. Rapid PD or threat to vital organs/critical anatomical sites (eg, spinal cord compression) requiring urgent alternative medical intervention, and/or continuation of study therapy would prevent institution of such intervention

Once unequivocal, confirmed PD is recognized, treatment with IMCgp100 must be discontinued.

Patients continuing treatment beyond the protocol-specified RECIST v.1.1 progression must provide separate consent to continue treatment after an initial assessment of PD. Treatment and assessments after an initial assessment of PD will continue to follow the treatment regimen of weekly IMCgp100.

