### 8.5 Investigator's Responsibilities

The investigator is responsible for the collection of AE data. All AEs should be recorded in the eCRF. The investigator shall report all SAEs immediately within 24 hours of being made aware of the event to Pharmacovigilance via the clinical database by completing as much information as possible and checking Yes when prompted whether the event is classified as an SAE in the AEs eCRF. The initial reporting can be supplemented by written reports using the SAE report form provided.

The follow-up reports (if required) shall identify the trial patients by unique code numbers assigned to the patient. The investigator shall supply the Sponsor with any additional requested information, notably for reported deaths of a patient.

All SAEs that occur between obtaining the patient's informed consent and 90 days after the last dose of study drug must be reported promptly to the CRO not later than 24 hours after the investigators or co-investigators become aware of their occurrence using the SAE eCRF in the study database.

The SAE eCRF is accessed via the study database. The following minimum information is required for the report:

- Patient identification (patient number and date of birth)
- Trial number
- Study treatment (dose, route, form, regime, start date, end date)
- Concomitant medication (including dose, route, form, regime, start date where available)
- Nature of SAE (overall diagnosis where available or alternatively signs and symptoms)
- Date and time of occurrence
- Any associated factors (concomitant disease or medication)
- Proposed relationship to study treatment
- Outcome
- Identify the reporter
- Action in relation to study (withdrawn from treatment, suspended, none)

The investigators or co-investigators are required to sign the SAE submission electronically in the clinical database within 24 hours of awareness of the event, even if the required information is incomplete or if the investigators are awaiting laboratory or diagnostic reports. Investigators may be asked for additional information for any reported SAE. An SAE follow-up report with attached documents (if necessary) should be forwarded to CRO Pharmacovigilance as soon as the additional information is available by email. The study number IMCgp100-401 must be in the title of any email for study identification purposes.

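### For patients continued on IMCgp100 after initial PD, Section 8.1.1 can exempt a death from SAE reporting on RECIST evidence that Section 6.6.1 does not treat as unequivocal

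*Protocol*

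**What the plan says.** Protocol Section 8.1.1 makes any AE serious if it "Is fatal or life-threatening". It then carves out one kind of death: "Death due to the progression of malignancy should not be reported as a SAE, if documented by use of appropriate method". The example given is "eg, as per Response Evaluation Criteria in Solid Tumors v.1.1.1". The sentence after that limits the carve-out: "Any AE that occurred as a result of the PD should be reported in the appropriate manner".

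The Amendment 2 rationale describes radiographic progression seen early on immunotherapy, IMCgp100 included. It says "This delayed response to therapy or immune-mediated tumor flare have been coined as" pseudo-progression, and that stabilization or response can follow. Section 2.4 carries the premise into the current text: initial progression can precede benefit, and such cases were seen in Phase I of this drug.

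Section 6.6.1 acts on that premise: "Upon disease progression by standard RECIST v.1.1 criteria, treatment beyond progression is an option". Patients who continue stay on weekly IMCgp100. For them, PD counts as unequivocal and confirmed only after a repeat scan 4 to 12 weeks later shows a further 20% increase in tumor burden over the initial PD assessment.

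On timing, Section 8.5 says that SAEs arising between consent and "90 days after the last dose of study drug must be reported promptly to the CRO", no later than 24 hours after the site becomes aware of them.

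**The concern.** The protocol applies two standards of evidence to the same scan. For deciding whether a patient's disease has truly progressed, an initial RECIST v1.1 PD is provisional. For deciding whether a death needs an SAE report, the same scan can serve as sufficient documentation. Section 8.1.1 mentions neither confirmation nor irRECIST, and does not ask whether the study drug may have contributed.

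The mismatch falls on the patients for whom the distinction matters most. Someone continued under Section 6.6.1 already has the PD scan and is still being dosed. If that patient dies and the site records disease progression and nothing else, nobody is prompted to ask whether the event was immune-mediated. The study's primary objective is to count patients with AEs associated with IMCgp100, so a route by which a possibly related death escapes causality review deserves closing.

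**Working it through.** There is no sample size, event rate or power figure to reproduce (Protocol Section 9.9 states that no formal sample sizing applies). The check is textual, with one interval.

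1. **Conditions of the exemption (8.1.1).** There are two: the death must be due to progression of malignancy, and the progression must be documented by an appropriate method. RECIST is an example of such a method. The version printed, v.1.1.1, appears nowhere else in the protocol. I read it as a slip for v1.1.

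2. **What a patient treated beyond progression already holds.** Entry to treatment under 6.6.1 requires a RECIST v1.1 PD. The documentation condition can therefore be met from the first day of continued treatment. Only attribution to progression remains, and that is the investigator's judgement.

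3. **When confirmation can arrive.** The repeat scan falls at 4 × 7 = 28 to 12 × 7 = 84 days after initial PD. A patient who dies before it has unconfirmed PD by the protocol's own definition. A patient whose repeat scan shows less than the further 20% increase also remains unconfirmed, so the exposed period can run past day 84.

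4. **What the exemption switches off.**
   - The 24-hour report in Section 8.5 applies to SAEs.
   - Causality under Section 8.3.1 is assessed for AEs. The bar is low: an effect that is improbable but not impossible is possibly related, and is pooled with related. A death recorded only as progression is never put to that test.
   - Protocol Section 9.6.1.1 lists and tabulates the deaths that are reportable as SAEs.
   - SAP Section 15.1.4 identifies fatal TEAEs from Grade 5 or the death seriousness box. Without a fatal AE record neither exists.

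5. **What remains on.** The death is still listed from the Death eCRF page (SAP Section 15.2) and counts as an event in OS (SAP Section 14.1). Neither route has a 24-hour clock or a causality field described in the documents.

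6. **Effect on AE incidence.** Incidence is by patient, and SAP Section 15.1 counts a patient once per category. A patient with any other TEAE is already in the overall count, so losing the fatal record changes the fatal and serious categories much more than overall incidence.

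**The case against.** The strongest reply is that most of what one would fear is already reportable. All AEs are collected through 90 days regardless of relationship (Section 8.1). An AE resulting from PD must be reported, and a fatal AE is serious. A patient who deteriorates through organ compromise, the kind of event item 4 of Section 6.6.1 foresees, would normally have a life-threatening or hospitalizing AE on record before death. That stands, and it confines the gap to deaths with no separate fatal AE entered.

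Several stronger readings are tempting, and the documents do not support them:

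- *Every death in a patient with a PD scan is exempt.* This is not so. The scan meets only the documentation condition. A death from cytokine release, sepsis or a cardiac event is not exempt, and neither is one the investigator attributes to flare. What all such patients hold is the scan, not the exemption.
- *The protocol describes a drug-induced, potentially fatal flare.* It says immune-mediated, describes a course that can end in stabilization or response, and reports no fatal case. Section 6.6.1 adds that only a minority benefit after initial PD, so most such progression may well be real.
- *RECIST v1.1 is the mandated standard.* It is an example. A site could apply irRECIST under the same words. The difficulty is that nothing requires it.
- *These deaths vanish from the data.* They remain in the deaths listing and OS.

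It may also be said that flare could be an AESI in the Investigator's Brochure, which is not available here. Section 8.1.1 defines an AESI as a kind of AE, so that route would still need an AE record.

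**Conclusion.** The inconsistency is real and limited. Section 8.1.1 accepts, for exempting a death, evidence that Sections 2.4 and 6.6.1 do not treat as unequivocal. It bites only when all of these hold: the patient was continued on IMCgp100 after initial RECIST v1.1 PD; death occurred on treatment or within 90 days of last dose; PD had not been confirmed; and the death was recorded only as disease progression. The mechanism is possible misattribution, because an initial RECIST v1.1 scan alone cannot separate flare from growth.

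The number of such deaths is unknown, since the documents give neither the uptake of treatment beyond progression nor a death rate. The loss is in expedited reporting, causality review and the fatal-TEAE listing. The effect on overall AE incidence is probably small.

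This rests on two assumptions: that a site would read the RECIST example as accepting a single unconfirmed PD, and that no site instruction outside these documents already says otherwise.

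**What to change.** Amend the one bullet in Section 8.1.1 so that it agrees with Section 6.6.1. For patients treated with IMCgp100 beyond initial RECIST v1.1 PD, a death on treatment or within 90 days of last dose is exempt from SAE reporting only if PD was unequivocal and confirmed as Section 6.6.1 defines it. Any other death in that group and period is reported as an SAE within 24 hours with a causality assessment.

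Leave the exemption as it is for patients who stopped IMCgp100 at initial PD. Section 6.6.1 defines confirmation only for those who continue, so applying it to everyone would make patients who stopped unable to qualify and would turn their genuine progression deaths into SAEs.

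Correct the RECIST version reference at the same time.

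The cost is a short protocol amendment, a reminder to sites, and a few additional SAE reports for deaths that prove to be disease-related. The SAP derivations need no change: a death entered as a fatal SAE is picked up by SAP Sections 15.1.3 and 15.1.4 as written.

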## 8.2 Criteria for Expectedness

The concept of expectedness refers to events that may or may not have previously been observed and documented and not necessarily the known pharmacological properties of the medicine. An AE will be unexpected for purposes of regulatory reporting unless it is mentioned in the appropriate reference safety information within the current Investigator's Brochure for the investigational drug, even if it is a medical occurrence expected for the disease being treated.

## 8.3 Assessment of Causality

### 8.3.1 Causality Assessment Required for All Adverse Events

The investigator decides whether he or she interprets the observed AE as either related to disease, to the study medication, study procedure, or other concomitant treatment or pathologies. To assess the relationship of the AE to the study drug, the following terms are defined:

- (1) Related: A direct cause and effect relationship between the study treatment and the AE is likely
- (2) Possibly related: A cause and effect relationship between the study treatment and the AE has not been demonstrated at this time and is not probable, but is also not impossible
- (3) Unrelated: Without question, the AE is definitely not associated with the study treatment

All “related” and “possibly related” AEs and SAEs will be defined as related to study drug.

